### 3.4 Interventions

Two variations of TranS-C are tested in the present research: Standard TranS-C and Adapted TranS-C. Both are delivered alongside the usual care offered by each CMHC. The control condition is usual care followed by delayed treatment with Adapted or Standard TranS-C (UC-DT). In the CMHCs, usual care consists of working with a service provider (e.g., psychologist, case manager, occupational therapist, psychiatrist, nurse practitioner) who provides direct mental health support from within their scope of practice. The patient might also be referred by that provider for other services as needed (e.g., healthcare, housing support, nutrition, vocational specialists, or peer advocacy). Occasionally patients receive treatment from interdisciplinary or residential teams, meaning their services are coordinated across multiple service providers. Although most providers delivered TranS-C via individual sessions, some chose to deliver it in a group setting. Note that TranS-C was originally developed in English, then translated into Spanish about four months into data collection to expand access and subsequently offered by Spanish-speaking providers. The treatment conditions, along with the adaptation process for Adapted TranS-C, are described below.

#### 3.4.1 Standard TranS-C

Standard TranS-C is delivered by CMHC providers across eight 50-minute, weekly sessions [40]. It is comprised of 4 cross-cutting modules featured in every session, 4 core modules, and 7 optional modules that are used based on clinical presentation, treatment goals, and provider case conceptualization. The *cross-cutting modules* are case formulation, sleep and circadian education, motivational enhancement, and goal setting. *Core module 1* targets irregular sleep-wake times, difficulty winding-down, and difficulty waking-up. *Core module 2* aims to reduce daytime impairment. *Core module 3* focuses on unhelpful beliefs about sleep. *Core module 4* aims to promote maintenance of changes made during treatment. *Optional module 1* addresses poor sleep efficiency via stimulus control [64] and sleep restriction [65]. *Optional module 2* helps patients reduce time in bed. *Optional module 3* addresses delayed or advanced phase problems (e.g., going to sleep later than desired or waking up earlier than desired). *Optional module 4* helps patients manage worries about sleep. *Optional Module 5* promotes compliance with Continuous Positive Airways Pressure (CPAP) for patients with sleep apnea. *Optional Module 6* helps patients negotiate sleep in complicated environments (e.g., noise from bed/roommates, traffic noise, streetlight entering the bedroom). *Optional Module 7* is for patients who experience nightmares. Training for the Standard TranS-C condition consists of a 1-day workshop (i.e., 6-8 hours) or two, 3-hour training blocks.

#### 3.4.2 Adapted TranS-C

Adapted TranS-C is delivered by CMHC staff across four, 20-minute, weekly sessions. Treatment consists of the same four *cross-cutting and core modules* as in Standard TranS-C, but the core modules are split up into five, rather than four, modules. *Core module 1* targets irregular sleep-wake times. *Core module 2* targets difficulty winding down. *Core module 3* targets difficulty waking up. *Core module 4* aims to reduce daytime impairment. *Core module 5* promotes maintenance of change. The one *optional module* focuses on reducing sleep-related worry and can be integrated with the core modules, based on clinical presentation, treatment goals, and provider case conceptualization. Training for the Adapted TranS-C condition consists of four, 1-hour workshops or two, 2-hour workshops, based on CMHC preferences.

There have been calls for rigorous approaches to treatment adaptation [66, 67]. In response, we grounded the process for adapting TranS-C in theory, data, and stakeholder input. As the overarching guide for the adaptation process, the Replicating Effective Programs (REP) framework [47] was used. Phase 1 of REP (Pre-Condition) was completed prior to the present protocol. First, as discussed above, we established that

there is a need for effective, feasible EBPTs for SMI in CMHCs and that sleep and circadian functioning may represent a powerful target to help address this need. Second, we determined that there was empirical support for TranS-C in CMHCs [35]. Third, we gathered stakeholder input on fit and packaging of the intervention [46, 50]. Fourth, we reviewed past data and identified the TranS-C treatment skills that were most utilized by patients with a utilization scale adapted from [68]. Fifth, we considered TranS-C's theoretical underpinnings and mechanisms of action [40, 41] from which we retained the core elements [66, 69]. Sixth, we piloted Adapted TranS-C with 21 adults through the PI's UC Berkeley research clinic (unpublished data). Informal feedback was solicited from providers and patients who participated in this pilot to further refine Adapted TranS-C. In Phase 2 of REP (Pre-Implementation), we customized the delivery of TranS-C training and treatment materials to the CMHC context based on the input from CMHC leadership, staff, and patients [46, 50]. Throughout REP Phases 1 and 2, following leading adaptation frameworks, we sought to ensure that Adapted TranS-C would be relevant to the broadest range of patients and to account for factors that impact implementation (e.g., resources required) [66, 70, 71]. The present trial will address the last two phases of REP – namely, Phases 3 (Implementation) and 4 (Maintenance and Evolution).

### 3.4.3 UC-DT

In UC-DT, patients begin with usual care for four weeks if their CMHC is randomized to Adapted TranS-C and eight weeks of usual care if their CMHC has been randomized to Standard TranS-C. After the delay, they receive Adapted or Standard TranS-C, also based on the condition to which their CMHC has been randomized (see Figure 2). The decision to compare TranS-C to UC-DT was made in close collaboration with the early CMHC partners. This design aims to strike a balance between (a) including a comparison group to demonstrate the effectiveness of TranS-C in community settings; (b) ensuring that *all* participants receive what we hypothesize to be an active treatment (TranS-C); and (c) maximizing efficiency in terms of study duration, budget, and participants' time investment. Notably, usual care has been the comparison group in several influential studies [72-74].

## 3.5 Measures

In addition to the measures below, a sociodemographics form is completed by providers and patients. Only measures that will be analyzed for the primary aims of the Implementation Phase (see above) are reported below. See Table 1 for timing of each measure.

### 3.5.1 Providers

#### 3.5.1.1 Primary Outcomes

*Acceptability.* Providers rate the acceptability of TranS-C via the *Acceptability of Intervention Measure* [75]. This 4-item measure is rated on a scale from 1 (completely disagree) to 5 (completely agree). This measure has demonstrated satisfactory known-groups validity, internal reliability, test-retest reliability, and sensitivity to change [75].

#### 3.5.1.2 Secondary Outcomes

*Appropriateness and Feasibility.* Providers rate the appropriateness and and feasibility of TranS-C via the following 4-item measures: *Intervention Appropriateness Measure* and *Feasibility of Intervention Measure* [75]. Both measures are rated on a scale from 1 (completely disagree) to 5 (completely agree). These measures have demonstrated satisfactory known-groups validity, internal reliability, test-retest reliability, and sensitivity to change [75].

### 3.5.1.3 Other Measures

*Number of TranS-C Sessions.* The number of sessions delivered to each enrolled patient by each provider will be counted.

*Occupation.* Providers are asked to report their current position, professional degree, and work history, including their caseload, theoretical orientation, licensure status, and previous training in sleep treatment.

## 3.5.2 Patients

### 3.5.2.1 Primary Outcomes

*Sleep Disturbance.* The 8-item PROMIS-Sleep Disturbance (PROMIS-SD) assesses disruption to sleep (e.g., restlessness, trouble staying asleep) over the past seven days [62]. Items are rated on a scale from 1 (not at all/never/very poor) to 5 (very much/always/very good), and scores range from 8-40, with higher scores indicating greater disturbance. This measure has demonstrated acceptable reliability and validity [61, 62].

### 3.5.2.2 Secondary Outcomes

*Sleep-Related Impairment.* The 16-item PROMIS-Sleep Related Impairment (PROMIS-SRI) assesses daytime impairment related to sleep problems over the past seven days on a scale from 1 (not at all/never) to 5 (very much/always) [62]. Scores range from 16-80, with higher scores indicating greater impairment (e.g., daytime sleepiness, difficulty concentrating). This measure has demonstrated excellent psychometric properties [61, 62].

*Functional Impairment.* Functional impairment is assessed via the Sheehan Disability Scale (SDS) [76]. Impairment in work and school, social life, and home and family is rated on a scale from 0 (not at all) to 10 (extremely). Scores range from 0-30, with higher scores indicating greater impairment. This measure has demonstrated good reliability and validity [76, 77].

*Overall Sleep Health.* The Sleep Health Composite is proposed to capture overall sleep health for the complexity of sleep problems in SMI that are covered by TranS-C [78]. It is defined as the sum of scores on six sleep health dimensions (each dimension dichotomized as 1 = good; 0 = poor): Regularity (midpoint fluctuation), Timing (mean midpoint), Efficiency (sleep efficiency), Duration (total sleep time), Satisfaction (sleep quality question on PROMIS-SD), and Alertness (daytime sleepiness question on PROMIS-SRI). All dimensions – except Satisfaction and Alertness – are assessed via questions about sleep-wake patterns over the past seven days (e.g., *In the past week, what time have you usually woken up in the morning?*). Scores range from 0-6, with higher scores indicating better sleep health. Initial validity of this measure has been established [78].

*Psychiatric Symptoms.* The DSM-5 Cross-Cutting Measure assesses psychiatric symptoms across 13 mental health domains. Participants rate how often they were bothered by each symptom on a scale from 0 (not at all) to 4 (nearly every day). Scores range from 0-52, with higher scores indicating more severe symptoms. This measure has demonstrated good test-retest reliability and clinical utility [79, 80].

### 3.5.2.3 Exploratory Outcomes

*PhenX Toolkit: Substance Use and Suicidality.* Scales from the PhenX Toolkit [81] are used to assess various patient outcomes, including suicidal ideation and behaviors, alcohol, tobacco, and other

psychoactive substances (e.g., cannabis, hallucinogens, sedatives, etc.). PhenX measures have been compiled by working groups and domain experts via a consensus process to facilitate consistency across studies [81]. To assess suicidal ideation and behaviors, the PhenX ‘Classification of Suicidal Ideation and Suicidal Behavior – Adult – Current’ protocol is used. This protocol includes two subscales from the screening version of the Columbia-Suicide Severity Rating Scale: Severity of Suicidal Ideation and Suicidal Behavior, assessing suicidality during two time periods—namely ideation in the past month and suicidal behavior in the past three months. To ease patient burden, this measure was adapted slightly, such that if patients deny suicidal ideation, they are not required to answer questions about suicidal behavior. To assess alcohol, the PhenX ‘Alcohol – 30-Day Quantity and Frequency’ protocol is used. This protocol measures both quantity and frequency of alcohol consumption. To assess tobacco, the PhenX ‘Tobacco – 30-Day Quantity and Frequency – Adult’ protocol is used. This measure has three sets of question protocols: (1) a protocol for ‘Every-Day Smokers,’ (2) a protocol for ‘Some-Day Smokers,’ and (3) a protocol for ‘Former Smokers.’ If patients report that they have never smoked tobacco, this measure is skipped. To assess use of substances and other drugs, the PhenX ‘Substances – 30-Day Frequency’ protocol is used. This measure assesses use of substances such as sedatives, painkillers, stimulants and hallucinogens. In addition, caffeine is assessed using questions adapted from the ‘Supplemental Beverage Questionnaire.’ Questions used in the present study assess frequency and quantity of caffeinated or decaffeinated drinks consumed over the past 30 days.

*Credibility and Perceived Improvement.* Perceptions of TranS-C credibility and symptom improvement are assessed by four questions adapted from the Credibility/Expectancy Questionnaire (CEQ) [82]. These questions assess (1) how logical TranS-C seemed, (2) how successful it was in reducing sleep symptoms, (3) how confident patients would be in recommending TranS-C to a friend, and (4) how much improvement patients believe had occurred. All questions are rated on a scale from 0 (not at all) to 9 (very), except for perceived improvement, which is rated as a percentage from 0-100%.

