#### **4.7 Exploratory Aim 1: TranS-C Treatment Condition on Credibility and PhenX Toolkit**

MLM will be used to test TranS-C treatment condition (Adapted vs. Standard TranS-C) predicting PhenX Toolkit outcomes of substance use and suicidality at post-treatment and 6FU. The approach to MLM will mirror Aim 2, except the outcomes will be substance use and suicidality from the PhenX Toolkit. Linear regression will be used to test treatment condition (Adapted vs. Standard TranS-C) predicting patient perceptions of TranS-C's credibility at post-treatment.

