## **6 TRIAL STATUS**

Protocol version 1, December 12, 2022. Data collection started in February 2020. Recruitment was completed in August 2022, but patient visits/assessments will continue through August 2023. Publishing of this protocol was delayed because of unforeseen challenges and uncertainties related to the COVID-19 pandemic and subsequent mandates (e.g., shelter-in-place), which began in California shortly after data collection started for this study.

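### Suicidal behavior (exploratory): a one-month ideation answer gates a three-month behavior question, and at post-treatment the look-back reaches before treatment by unequal shares in Adapted and Standard TranS-C

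*Combined protocol and SAP*

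**What the plan says.** Section 3.5.2.3 of the combined protocol and SAP places suicidality among the exploratory patient outcomes. Its two subscales cover "ideation in the past month and suicidal behavior in the past three months". To lighten the assessment, the measure was altered so that "if patients deny suicidal ideation, they are not required to answer questions about suicidal behavior". One month is the only ideation window described. Neither this section nor section 4.7 says how an unanswered behavior item is scored.

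Section 4.7 plans multilevel models of Adapted versus Standard TranS-C "predicting PhenX Toolkit outcomes of substance use and suicidality at post-treatment and 6FU". They follow the Aim 2 models, in which the effect of interest is the treatment-by-time interaction. Section 4.7 does not say whether suicidality means ideation, behavior or both. Table 1 schedules the PhenX measures at pre-treatment, post-treatment and 6FU.

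The versions differ in planned length. Section 3.4.1: "Standard TranS-C is delivered by CMHC providers across eight 50-minute, weekly sessions". Section 3.4.2: "Adapted TranS-C is delivered by CMHC staff across four, 20-minute, weekly sessions". The delayed-treatment arm in section 3.4.3 follows the same pattern: "usual care for four weeks if their CMHC is randomized to Adapted TranS-C and eight weeks of usual care" at Standard sites. Section 6 reports that recruitment closed in August 2022 and that "patient visits/assessments will continue through August 2023".

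**The concern.** There are two separate problems.

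**The gate.** A question about the last month decides whether a question about the last three months has to be answered. A patient with suicidal behavior in month two or three who denies ideation in the last month may leave no record of it. These are patients whose ideation has recently resolved, which is the pattern an effective treatment would produce.

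**The look-back.** Three months is longer than either treatment, so the behavior window at post-treatment reaches back before the first session, and further in the shorter version. Events that treatment could not have influenced then enter the post-treatment outcome in unequal amounts. If the pre-treatment visit falls at treatment start, the same weeks were already covered there, so one event can count at both visits.

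At stake is the between-version reading of suicidal behavior at post-treatment, in a trial that accepts patients with suicidal ideation (section 3.2).

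**Working it through.** The plan states no figure on this point, so there is none to reproduce. The check is arithmetic on the recall windows.

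**Inputs**
- Behavior look-back L: three months (section 3.5.2.3), taken as 13 weeks; 12 weeks also tried.
- Ideation look-back: one month, taken as 30 days.
- Weeks t from treatment start to the post-treatment visit: 4 in Adapted and 8 in Standard (sections 3.4.1 to 3.4.3). Counting from first to last weekly session gives 3 and 7.
- 6FU: six months after treatment (section 3.6.2), about 26 weeks.

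**Step 1. Pre-treatment share of the behavior window** = (L − t) / L

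| L, t (Adapted/Standard) | Adapted | Standard |
|---|---|---|
| 13, 4/8 | 9/13 = 69% | 5/13 = 38% |
| 13, 3/7 | 10/13 = 77% | 6/13 = 46% |
| 12, 4/8 | 8/12 = 67% | 4/12 = 33% |
| 12, 3/7 | 9/12 = 75% | 5/12 = 42% |

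In each on-schedule variant, Adapted is above one half and Standard below it. At 6FU, 26 weeks exceeds 13, so the share is 0% in both.

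**Step 2. Late visits.** With the visit d weeks late and L = 13, the shares are (9 − d)/13 and (5 − d)/13, not below zero. At d = 2.5 they are 50% and 19%; at d = 4, 38% and 8%. With equal delay in both versions the gap stays at 4/13 = 31 percentage points up to d = 5, then narrows, and closes at d = 9.

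**Step 3. Effect on the comparison.** Assume a constant event rate that is multiplied by r from treatment start, with the same r in both versions. The expected ratio of post-treatment to pre-treatment events is (9 + 4r)/13 in Adapted and (5 + 8r)/13 in Standard.

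| r | Adapted | Standard |
|---|---|---|
| 0.25 | 0.77 | 0.54 |
| 0.50 | 0.85 | 0.69 |
| 0.75 | 0.92 | 0.85 |

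An identical benefit appears larger in Standard.

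**Step 4. Ideation at post-treatment.** With 28 days of Adapted treatment, a 30-day window reaches about 2 days before treatment; with 56 days of Standard it does not reach back at all. If the visit came on the day of the last Adapted session (21 days), the overlap would be 9 of 30 days, so this step depends on the four-week interval.

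**Step 5. The gate.** Months two and three make up 2/3 of the behavior window and have no ideation item of their own. Suppose that behavior is spread evenly over the three months, that past-month behavior always comes with reported ideation, and that unanswered items are scored as none. If a fraction q of patients with behavior in months two or three still report past-month ideation, the share of behavior missed is (2/3)(1 − q): 7% at q = 0.9, 20% at 0.7, 33% at 0.5 and 47% at 0.3. The documents give no value for q, so this is a range under assumption and not an estimate.

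**The case against.** Several stronger readings are tempting, and the documents do not support them.

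- **That behavior is undercounted.** No scoring rule is stated, and section 4.1 says that all available data are used. If unanswered items become missing, the result is a sample selected on current ideation, not an undercount. The text also says that patients need not answer, which is weaker than saying they are never asked.
- **That the gate itself biases Adapted against Standard.** The rule is described without distinction by version or visit. Alone it distorts the comparison only if past-month ideation differs between versions, and the documents give no figure for that. It is the look-back that breaks comparability.
- **That behavior is certain to be the outcome tested.** Section 4.7 says only suicidality. Ideation severity may already be what is meant, in which case the plan needs to say so.
- **That 69% and 38% will be the realized shares.** They hold on schedule. Section 4.6 allows for assessments months off target, and section 5 describes turnover and discontinuity. Step 2 shows that lateness lowers both shares, but an equal delay removes the gap only at nine weeks.
- **That safety monitoring fails here.** The measure is an exploratory outcome taken at three visits. Oversight rests elsewhere: the monitoring board in section 3.9, and the provider contact and medical-record access required by section 3.2.
- **That the gate can simply be dropped now.** Recruitment closed in August 2022 and the protocol is dated December 2022. A Standard delayed-treatment patient enrolled last reaches post-treatment about 8 + 8 = 16 weeks later, around late December, so the visits still open are mainly 6FU. Gated baselines would then be set against partly ungated follow-up. Standard patients reach 6FU 4 weeks later than Adapted if treated immediately and 16 − 8 = 8 weeks later if delayed, so for similar enrolment dates more Standard visits would be ungated.

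The gate also has a disclosed reason, patient burden, and section 5 reports that some patients found the assessments long. What stands after all this is an unspecified variable, an unspecified scoring rule, and unequal look-backs at one of the two analysis times.

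**Conclusion.** The point holds in limited form. The skip rule can leave behavior in months two and three unrecorded. Whether that produces an undercount or a selected sample depends on a coding rule that the plan does not give, and its size is not derivable from the documents. Separately, a post-treatment comparison of behavior between versions is not like for like: 69% against 38% of the window precedes treatment, given a 13-week look-back and on-schedule visits. The direction, equal effects looking larger in Standard, rests on a constant underlying event rate and a benefit that starts with treatment. Behavior at 6FU is free of the look-back problem, though still gated. Past-month ideation at post-treatment is essentially free of it if the visit falls about four weeks or more after the first session. Because the outcome is exploratory, no primary or secondary result, multiplicity adjustment or sample-size claim depends on it. The correction belongs in the analysis plan and is worth making because it is cheap and specific.

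**What to change.** In section 4.7:

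1. Name the suicidality variables. Use past-month ideation severity at post-treatment.
2. Compare suicidal behavior between versions only at 6FU.
3. Record unasked behavior items as not assessed, never as zero by default. Report how many patients were not asked, by visit and version. Show the 6FU comparison under both codings: unasked as missing, and unasked as no behavior, the latter labelled as an assumption.
4. If the behavior items are put to every patient at the remaining visits, use the added answers descriptively only. Keep the existing skip rule for the between-version comparison, so that a mid-trial change does not create differential ascertainment.

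Items 1 to 3 need only plan wording and a tabulation, with no new data. Item 4 is optional and slightly lengthens the visits. The cost is that there is no between-version result for behavior at post-treatment, for an exploratory outcome. Behavior left unasked at past visits cannot be recovered by any analysis.
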